## 5. Research Plan:

### A. Overview

The proposed study will assess the effects of the COMT inhibitor, tolcapone, versus placebo on reducing withdrawal symptoms (including cognitive decrements), smoking urges and smoking behavior, in women smokers. This will be a double-blind, placebo-controlled study, with 60 women smokers. After completing an *ad libitum* smoking baseline, participants will be randomized to 8-days of the COMT inhibitor tolcapone (100mg three times a day (TID) for 7 days then 100mg once on day 8) or placebo (Apud *et al*, 2007; Grant *et al*, 2013). For the first two days of the medication period, participants will continue to smoke *ad libitum* and attend brief check-in sessions once daily to take one dose and be given the remaining two doses to take at home. On medication days 3-5, they will be given take-home doses and will be asked to check in daily by phone or in person and continue to smoke *ad libitum*. On the evening of medication day 5, the 60-hr (2 ½ day) abstinence period will begin. During the 2 ½ day abstinence period, participants will attend brief check-ins daily, to receive their dose (plus take-home doses) and to be screened for abstinence adherence (breath CO levels; urine cotinine). Measures of withdrawal and smoking urges will be collected at all sessions. On Medication Day 8, a test session will be conducted where assessment of cognitive function and smoking behavior will be collected. At the conclusion of the session on Medication Day 8, subjects will be stop the medication. A brief follow-up session will be completed approximately 1-week after the final medication day then subjects will be discharged from the study. A between-subject design will be used since the study involves numerous visits and several days of abstinence and we predict that a within-subject design would be overly burdensome to participants and result in high attrition rates. A between-subject design also avoids possible medication carryover effects.

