Minnesota Nicotine Withdrawal Symptom Checklist (MNWS): At all sessions except screening, smokers will be asked to rate nicotine withdrawal symptoms (cigarette craving, irritability/anger, anxiety/tension, difficulty concentrating, restlessness, increased appetite, depressed mood, and insomnia) on a 100 mm scale, "not at all" to "extremely" (Hughes and Hatsukami, 1986).

Brief Questionnaire on Smoking Urges (BQSU): This 10-item scale reliably measures cigarette craving (Tiffany and Drobes, 1991) and will be administered at all sessions except screening.

Positive and Negative Affect Schedule (PANAS): The PANAS is a 20-item scale that assesses both negative and positive affective states (Watson *et al*, 1988). This scale is sensitive to the affective symptoms of tobacco withdrawal and predicts relapse to smoking (Kenford *et al*, 2002) and will be administered at all sessions except screening.

Premenstrual Assessment Form (PAF): Given their potential overlap with withdrawal symptoms (Allen *et al*, 1996; Allen *et al*, 1999; Carpenter *et al*, 2006), premenstrual symptoms will be assessed with the 10-item PAF (Halbreich *et al*, 1982) at all sessions except screening so they can be used as covariate in analyses focusing on withdrawal symptoms.

Drug Effects Questionnaire (DEQ): Smokers will rate 10 items that are related to nicotine effect on a 100 mm scale, "not at all" to "extremely." The items are feeling "stimulated", "high", "anxious", "sedated", "down", "good drug effects", "bad effects", "drug strength" as well as

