### *Cognitive*

The Shipley Institute of Living Scale (SILS): This is a brief, well validated means of estimating intelligence quotient (IQ) (Zachary, 1991). The form consists of 60 items comprising 2 subscales, a vocabulary subscale (40 items) which asks subjects to indicate which of four words is most similar in meaning to the target word, and an abstract thinking subscale (20 items) wherein subjects are asked to fill in a letter or number to complete a pattern. The SILS will be administered at the screening session to check for baseline group differences, since cognitive measures are included as outcomes and are expected to differentially change with withdrawal across medication groups.

Computerized Testing: Cognitive testing, administered at *ad libitum* smoking baseline and the post-2 ½ day-abstinence final assessment, will include computerized tasks of sustained attention (ANAM Continuous Performance Task (CPT)); CANTAB Rapid Visual Information Processing (RVP)), executive function in including cognitive flexibility, cognitive control planning and decision-making (CANTAB Stockings of Cambridge (SOC), CANTAB Cambridge Gamble Task (CGT), ANAM Stroop); and memory/learning (Hopkins Verbal Learning Task (HVLT); Digit Span) (Owen *et al*, 1991) (Owen *et al*, 1990) (Wechsler, 2008) (Brandt, 1991) (Reeves *et al*, 2002). Parallel task versions will be used where available. These tasks were chosen for the cognitive domains’ sensitivity to DA(Ersche *et al*, 2011; Harmer *et al*, 2001; Lange *et al*, 1992; Levin *et al*, 2011; Mehta *et al*, 1999; Owen *et al*, 1992), or nicotine(Sahakian *et al*, 1989); engagement of PFC-striatal neurocircuitry (Chase *et al*, 2008; Clark *et al*, 2007; Cools *et al*, 2004; Ersche *et al*, 2011; Kim *et al*, 2006b; London *et al*, 2005; Mehta *et al*, 2000; Owen *et al*,

1991); impairment in smokers(Durazzo *et al*, 2012; Hughes, 2007); relevance to smoking outcomes(de Wit, 2009; Patterson *et al*, 2010); and proposed relevance as treatment targets for smokers(Sofuoglu *et al*, 2013).

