Official Title in ClinicalTrials.gov: Treatment for Nicotine Addiction in Women

NCT: NCT02448654

Document Date: 7/7/14

<from originally planned analysis section- from grant>

Sample Size Considerations and Data Analysis

Power Analysis: As this is the first randomized clinical trial evaluating the effect of tolcapone on withdrawal, smoking urges, and cognition in women smokers during abstinence, we used effect sizes from comparisons of Val158Met genotype as general proxies for treatment differences. In previous research, we found significant differences in women smokers by Val/Val vs. Met/_ genotype in withdrawal (F= 5.7, df=48, p=.02), smoking urges (F= 16.9, df=48, p<.001), and sustained attention (F=9.9, df=48, p=.003) during abstinence, and subjective ratings of nicotine's anxiolytic effects (F=3.7, df=47, p=.02) (see Preliminary Data). Using G*Power, we found that with a sample of 60, alpha=.05, power=.80, we would be able to detect large effects for our planned analyses (f=.37). We expect to enroll 80 subjects to achieve a completion N=60. However, with N=52 we would still be able to detect a large effect size (f=.40).

Analysis Plan: The primary statistical models will be analysis of covariance (ANCOVA) to test for medication group differences in withdrawal, smoking urges, sustained attention and smoking choice post-abstinence. COMT genotype will be used as an independent variable in an exploratory two factor ANCOVA. Menstrual cycle phase, race and baseline smoking severity will be included as covariates.

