Specific Aim 1: ANCOVAs will examine the effect of tolcapone on reducing a) withdrawal severity (MNWS); b) smoking urges (BQSU); and c) cognitive impairment (e.g., CPT) during abstinence vs. placebo. With 80% power, we can detect a large medication effect (f=.37). Specific Aim 2: ANCOVA will examine the effect of medication vs. placebo on laboratory smoking choices post-abstinence. With 81% power, we can detect a large effect (f=.40). Exploratory Aim 1: ANCOVAs will examine the effect of Met/_ genotype on reduced a) withdrawal severity (MNWS); b) smoking urges (BQSU); and c) cognitive impairment (e.g., CPT) during abstinence vs. Val/Val. With 80% power, we can detect a large genotype effect (f=.37). Exploratory Aim 2: ANCOVA will assess withdrawal and smoking post abstinence, using both medication and genotype as the independent variables and co-varying for baseline scores, to test for a medication by genotype interaction. With 81% power, we can detect a large effect (f=.40).

Exploratory Aim 3: Structural equation modeling will examine moderating effects of gonadal hormone levels on withdrawal severity and smoking behavior post-abstinence. The mediation effect size is unknown.

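### The Aim 1 ANCOVAs do not name the outcome's own pre-randomisation baseline as a covariate, although it is collected: a possible loss of precision, not of validity

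*SAP*

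**What the plan says.** The SAP's Analysis Plan names ANCOVA as the primary model for four post-abstinence outcomes: withdrawal, urges, sustained attention and smoking choice. Its covariate sentence reads: "Menstrual cycle phase, race and baseline smoking severity will be included as covariates". The Specific Aim 1 text lists MNWS, BQSU and "c) cognitive impairment (e.g., CPT) during abstinence vs. placebo" and adds no covariate.

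Baseline scores appear only in Exploratory Aim 2, the medication-by-genotype test: "ANCOVA will assess withdrawal and smoking post abstinence, using both medication and genotype as the independent variables and co-varying for baseline scores". That sentence covers withdrawal and smoking; it does not name urges or attention.

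The protocol collects the missing baselines:

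- MNWS: "At all sessions except screening, smokers will be asked to rate nicotine withdrawal symptoms".
- BQSU: "reliably measures cigarette craving (Tiffany and Drobes, 1991) and will be administered at all sessions except screening".
- Attention: the testing done at both the ad libitum baseline and the final session includes "computerized tasks of sustained attention (ANAM Continuous Performance Task (CPT)); CANTAB Rapid Visual Information Processing (RVP".

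The order of events is clear from the Overview: after the ad libitum "smoking baseline, participants will be randomized to 8-days of the COMT inhibitor tolcapone". The description of the Day 8 session in Study Procedures repeats the baseline questionnaires and tasks.

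**The concern.** A score taken before randomisation on the same instrument is usually the first covariate to consider in an ANCOVA of the later score. Here it is available for every Aim 1 outcome at no extra burden, yet the primary models do not mention it. Baseline smoking severity does not replace it, because that describes smoking and not the baseline MNWS, BQSU or attention score.

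Two things are at stake. The first is precision: the SAP says that the trial can detect only large effects, so unexplained outcome variance is expensive. The second is pre-specification. One exploratory model for withdrawal is baseline-adjusted, while the primary model for the same outcome is silent. An analyst could defend either choice after seeing the data.

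For attention there is a further gap. The SAP gives CPT only as an example and the protocol also collects RVP, so neither the outcome nor its baseline is fixed.

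**Working it through.** **Inputs.** From the SAP: alpha .05; N=60 with f=.37 at power .80; N=52 with f=.40; withdrawal proxy "genotype in withdrawal (F= 5.7, df=48, p=.02"). Assumed, because the documents do not give them: a two-sided test, two equal arms, each listed covariate as one model column, and r, the partial correlation between baseline and outcome given the listed covariates.

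**Formula.** Noncentral F with numerator df 1, denominator df = N − 2 − k, and noncentrality λ = N·f²/(1 − r²). Without the baseline, k=3 and r=0. With it, k=4.

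**The plan's own figures.** For N=60 and f=.37, λ = 60 × .1369 = 8.214 on 1 and 55 df. Power is 80.4%, and detectable f at 80% power is .368. For N=52 and f=.40, λ = 52 × .16 = 8.32 on 1 and 47 df, and power is 80.65%. Both stated figures reproduce without the baseline. Using k=0 or k=5 changes power by about 0.1 point or less.

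**Withdrawal proxy.** With 1 numerator df (two genotype groups), f = √(5.7/48) = .345. At N=60 without the baseline, power is 74.6%.

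**Adding the baseline.**

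| Assumed r | Power, N=60, f=.37 | Detectable f, N=60 | Power, N=52, f=.40 | Power, withdrawal proxy, N=60 |
|---|---|---|---|---|
| not in model | 80.4% | .368 | 80.65% | 74.6% |
| 0 | 80.4% | .368 | 80.6% | 74.6% |
| .1 | 80.8% | .366 | 81.0% | 75.0% |
| .2 | 81.9% | .361 | 82.2% | 76.3% |
| .3 | 83.9% | .351 | 84.1% | 78.5% |
| .5 | 90.2% | .319 | 90.3% | 85.7% |

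The withdrawal proxy reaches 80% power at r of about .35.

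**Cost of adjusting.** The lost degree of freedom alone costs about 0.02 points at N=60 and r=0 (.8039 to .8037). A baseline that is not balanced by the randomisation also differs between arms by chance, which inflates the adjusted standard error. This is allowed for by multiplying λ by a Beta((N−2)/2, 1/2) variable, with the listed covariates treated as balanced by the urn. At N=60 and f=.37, power is then 79.7, 80.1, 81.3, 83.3 and 89.6% for r = 0, .1, .2, .3 and .5. The worst case costs 0.7 points, and break-even is at r of about .13.

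**If f=.37 was already meant on a baseline-adjusted scale.** The model with baseline then has only the stated 80%. The model as written has effective f = .37·√(1 − r²), which gives 80.4, 80.0, 78.8, 76.6 and 68.4% for the same r values.

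**Validity.** In 20,000 simulated trials of 30 per arm per scenario, leaving the baseline out gave type I error of 5.2% (r=.5) and 5.0% (r=.7). Including it gave 5.0% and 5.1%. For a true difference of .74 SD, mean estimates were .740 without the baseline and .739 to .741 with it.

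**The case against.** The strongest reply is that the SAP is a short extract from a grant and that its covariate list is not complete. The protocol collects the Premenstrual Assessment Form for use as a covariate in withdrawal analyses, and estradiol and progesterone as covariates; neither is in the SAP list. Since Exploratory Aim 2 adjusts for baseline scores, adjustment may have been intended throughout. This is fair, and it makes the point one of unstated rather than rejected adjustment. It does not supply the missing statement. The extra covariates barely move power: with baseline included and r=0, k=7 gives 80.3%.

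Second, the other two proxies leave little to gain. By the same method without the baseline, urges (F=16.9, f = √(16.9/48) = .593) have 99.5% power and attention (F=9.9, f = √(9.9/48) = .454) has 93.3%. This stands, and it is why withdrawal is where the point matters most. The SAP itself offers these genotype contrasts only as rough stand-ins for a drug effect.

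Third, r is unknown and may be low, because baseline is taken while smoking freely and the outcome after about 60 hours of abstinence. This also stands. At r=.2 the gain is 1.5 points, or 0.9 with chance imbalance counted, and below about .13 there is a small loss. The gain is therefore conditional.

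Fourth, the choice between CPT and RVP is an outcome-definition gap in its own right. That is so, and the covariate point does not depend on it. It matters here only because a baseline term for attention cannot be written until the task is named.

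**Conclusion.** The concern holds. The Aim 1 models do not name the outcome's own baseline, which is collected before randomisation on the same instruments. Analysed as written, the comparison remains valid and the stated power is correct; no figure in the SAP is wrong on this account.

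The possible gain at N=60 and f=.37 runs from nothing at r=0 to about 10 points at r=.5, against a worst-case loss of about 0.7 points. These figures rest on the assumed r and on f=.37 being relative to the SD before baseline adjustment. If f=.37 is already on the adjusted scale, stating the covariate is needed to keep the claimed 80% once r exceeds about .1. The change should be made as a low-cost improvement; the trial does not depend on it.

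**What to change.** In the SAP, state that each Aim 1 ANCOVA includes the ad libitum baseline value of the same outcome: MNWS for withdrawal, BQSU for urges, and one named sustained-attention task and score, the same at both sessions. Keep the three listed covariates, which broadly match the urn factors (the SAP says smoking severity, the urn uses smoking rate). While editing, say whether the premenstrual and hormone measures that the protocol describes as covariates belong in these models.

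Do not extend this to Aim 2: the Smoking Choice Paradigm is run once, after abstinence, and has no baseline of its own.

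The cost is SAP wording, the choice of one attention score, and one residual degree of freedom per Aim 1 model. No new data are needed. The wording should be fixed before unblinding so that the covariate set cannot depend on the results.
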